### 3.0 LIST OF ABBREVIATIONS

AE	adverse event
ALCL	anaplastic large cell lymphoma
alloSCT	allogeneic stem cell transplant
ATA	antitherapeutic antibodies
CI	confidence interval
CR	complete remission
CSR	clinical study report
CT	computed tomography
CTCAE	Common Terminology Criteria for Adverse Events
DLT	dose-limiting toxicity
DOE	duration of response
ECG	electrocardiogram
ECOG	Eastern Cooperative Oncology Group
eCRF	electronic case report form
EFS	event-free survival
HL	Hodgkin lymphoma
IRF	independent review facility
IV	intravenous; intravenously
IWG	International Working Group
MedDRA	medical dictionary for regulatory activities
MMAE	monomethyl auristatin E
MTD	maximum tolerated dose
NCI CTCAE	National Cancer Institute Common Terminology Criteria for Adverse Events
ORR	overall response rate
OS	overall survival
PD	progressive disease
PET	positron emission tomography
PFS	progression-free survival
PK	pharmacokinetic(s)
PR	partial remission
RDI	relative dose intensity
RP2D	recommended phase 2 dose
SAE	serious adverse event
SAP	statistical analysis plan
sALCL	systemic anaplastic large-cell lymphoma
SCT	stem cell transplant
SD	stable disease
StdDev	standard deviation
TPP	time to progression
WHO	World Health Organization

## 4.0 OBJECTIVES

### 4.1 Primary Objectives

Phase 1 primary objectives are:

- To assess the safety profile and determine the pediatric maximum tolerated dose (MTD) and/or RP2D of brentuximab vedotin
- To assess the pharmacokinetics (PK) of brentuximab vedotin

Phase 2 primary objective is:

- To determine the best overall response rate (CR, PR) with brentuximab vedotin at RP2D

### 4.2 Secondary Objectives

Phase 1 secondary objectives are:

- To determine the immunogenicity of brentuximab vedotin
- To determine the best overall response rate (CR, PR) with brentuximab vedotin
- To determine the time to progression, time to response, duration of response, and event-free, progression-free, and overall survival with brentuximab vedotin

Phase 2 secondary objectives are:

- To determine the time to progression, time to response, duration of response, and event-free, progression-free, and overall survival with brentuximab vedotin
- To assess the PK and safety profile of brentuximab vedotin
- To determine the immunogenicity of brentuximab vedotin

### 4.3 Exploratory Objectives

Phase 1 exploratory objective is:

CCI  
[REDACTED]

Phase 2 exploratory objective is:

CCI  
[REDACTED]

## 4.4 Study Design

This is a phase 1/2, open-label, single-agent, multicenter, dose-escalation study of brentuximab vedotin in pediatric patients with relapsed or refractory sALCL or HL for which standard, curative, life-prolonging or palliative treatment does not exist or is no longer effective. The primary objectives of the study are to assess the safety and pharmacokinetics, determine the pediatric MTD and/or RP2D of brentuximab vedotin in pediatric patients, and evaluate the antitumor activity of brentuximab vedotin in eligible patients.

Approximately 42 evaluable patients will be enrolled in this study. In the phase 1 portion of the study, up to 12 patients with relapsed or refractory CD30+ malignancies (including HL and sALCL) will be enrolled in 2 planned dose cohorts (3 to 6 patients per cohort) according to the standard 3 + 3 dose escalation scheme.

Once the MTD and/or RP2D have been reached, patients will be enrolled by diagnosis into two phase 2 study arms: relapsed or refractory sALCL, or relapsed or refractory HL. A sufficient number of patients will be enrolled in the phase 2 portion of the study to have at least 15 evaluable patients with sALCL (including patients treated at the RP2D during phase 1), of whom at least 10 patients are in first relapse, and at least 15 evaluable patients with HL (including patients treated at RP2D during phase 1).

Brentuximab vedotin will be administered by IV infusion once every 21 days. Each 21-day treatment cycle is composed of 1 day of study drug treatment, followed by a monitoring period of 20 days. The starting dose in phase 1 will be 1.4 mg/kg, and escalation will proceed using a traditional 3 + 3 design to a maximum dose of 1.8 mg/kg.

Overall response will be evaluated beginning after 2 cycles of therapy. Objective response over the course of the study will be assessed by an IRF according to the IWG Revised Response Criteria for Malignant Lymphoma [1]. Patients, including those who achieve a CR, a PR, or stable disease (SD), may receive brentuximab vedotin for up to 16 cycles. Treatment with brentuximab vedotin beyond 16 cycles may be permitted at the joint discretion of the sponsor and the investigator for those patients experiencing continued clinical benefit. Following administration of the final dose of brentuximab vedotin, patients will be monitored for adverse events for a minimum of 30 days. Patients will be followed for PFS and OS every 12 weeks for 12 months after the EOT visit. Thereafter, assessment for OS will continue every 6 months until the sooner of death or study closure or a maximum of 2 years after enrollment of the last patient. Patients who remain on treatment after Cycle 16 will be followed according to the above schedule or until study closure.

Study drug will be discontinued due to occurrence of unacceptable AE, progressive disease, patient withdrawal, or study termination. Patients may discontinue therapy at any time. Additionally, those patients who experience a CR and are candidates for hematopoietic stem cell transplantation must discontinue brentuximab vedotin prior to chemotherapy and transplant; these patients will be followed for survival analyses until study closure.

AEs will be assessed, and laboratory values, vital signs, and electrocardiograms (ECGs) will be obtained to evaluate the safety and tolerability of brentuximab vedotin.

Serial blood samples for determination of the concentration of brentuximab vedotin, total therapeutic antibody, and MMAE will be obtained during Cycle 1 and subsequent cycles at prespecified time points as described in the Schedule of Events (SOE) in the protocol.

Radiological evaluations, (CT scan or magnetic resonance imaging [MRI], and PET as clinically indicated), will be employed to assess the status of the patient's underlying disease. An evaluation of disease response will be assessed by an IRF according to the IWG Revised Response Criteria for Malignant Lymphoma [1] evaluated at Cycles 2, 4, 7, 10, 13, and 16 and

then at the end of treatment. The scan frequency for patients who receive treatment past Cycle 16 is outlined in the Schedule of Events. Additional evaluations may be necessary when clinically indicated.

## 5.0 ANALYSIS ENDPOINTS

### 5.1 Phase 1 Primary Endpoints

[figure not shown]
- Adverse events (AEs), serious adverse events (SAEs), assessments of clinical laboratory values, and vital signs measurements
- Serum concentrations of brentuximab vedotin, total therapeutic antibody, and plasma concentrations of MMAE

### 5.2 Phase 1 Secondary Endpoints

- Antitherapeutic antibody (ATA), ATA titer, and neutralizing ATA
- Best overall response rate (CR, PR) as determined by an independent review facility (IRF) using positron emission tomography (PET), computed tomography (CT), magnetic resonance imaging (MRI), and clinical assessment, according to International Working Group (IWG) revised response criteria
- Time to progression
- Time to response
- Duration of response
- Event-free survival
- Progression-free survival
- Overall survival

### 5.3 Phase 1 Exploratory Endpoints

CC1

### 5.4 Phase 2 Primary Endpoints

- Best overall response rate (CR, PR) as determined by an IRF using PET, CT, MRI, and clinical assessment according to IWG revised response criteria

### 5.5 Phase 2 Secondary Endpoints

- Time to progression
- Time to response
- Duration of response
- Event-free survival

- Progression-free survival
- Overall survival
- Adverse events, serious adverse events, assessments of clinical laboratory values, and vital signs measurements
- Serum concentrations of brentuximab vedotin, total therapeutic antibody, and plasma concentrations of MMAE
- Antitherapeutic antibody (ATA), ATA titer, and neutralizing ATA

## 5.6 Phase 2 Exploratory Endpoints

• CCI

## 6.0 DETERMINATION OF SAMPLE SIZE

Approximately 42 evaluable patients will be enrolled in this study. In the phase 1 portion of the study, up to 12 patients with relapsed or refractory CD30+ malignancies will be enrolled in 2 planned dose cohorts (3-6 patients per cohort), according to the standard 3 + 3 dose escalation scheme.

Once the MTD and/or RP2D have been reached, patients will be enrolled by diagnosis into two phase 2 study arms: relapsed or refractory sALCL or relapsed or refractory HL. A sufficient number of patients will be enrolled in the phase 2 portion of the study to have at least 15 evaluable patients with sALCL (including patients treated at the RP2D during phase 1), of whom at least 10 patients are in first relapse, and at least 15 evaluable patients with HL (including patients treated at the RP2D during phase 1).

The sample size is not based on statistical consideration. Based on the exact binomial confidence interval calculation, 10 responses observed out of the 15 evaluable patients (overall response rate of 66.7%) will provide a 95% confidence interval of (38%, 88%).

## 7.0 METHODS OF ANALYSIS AND PRESENTATION

### 7.1 General Principles

In general, descriptive statistics (number of observations, mean, standard deviation (StdDev), median, minimum, and maximum) will be used to summarize continuous variables. Frequencies and percentages will be used to summarize categorical variables. Time-to-event data will be analyzed using the Kaplan-Meier method and results will be summarized by the 25th, 50th (median), and 75th percentiles, if estimable, with associated 2-sided 95% confidence intervals, as well as the percentage of censored observations.

Unless otherwise specified, safety and efficacy data will be summarized in the following 7 groups: 1.4 mg/kg phase 1 only; 1.8 mg/kg phase 1 only; 1.8 mg/kg phase 1&2 HL only; 1.8 mg/kg phase 1&2 sALCL only; 1.8 mg/kg phase 1&2 sALCL in first relapse only; 1.8 mg/kg all patients; all patients. Pharmacokinetic analyses will be summarized by dose and treatment cycle.

The baseline value is defined as the value collected at the time closest to, but prior to, the start of study drug administration, unless otherwise specified. A windowing convention will be used to determine the analysis value for a given study visit for observed data analyses.

All available efficacy and safety data will be included in data listings and tabulations. Data that are potentially spurious or erroneous will be examined under the auspices of standard data management operating procedures. In general, there will be no imputation of missing data. For time-related endpoints, subjects who have no specified events will be censored as specified for each respective endpoint in Section 7.8. Imputation rules for missing dates of AEs and concomitant medications are detailed in Sections 7.1.3 and 7.1.4.

SAS Version 9.2 (or higher) will be used for all analyses.

#### 7.1.1 Definition of Study Days

Study Day 1 is defined as the date on which a subject is administered their first dose of the medication. Other study days are defined relative to the Study Day 1 with Day 1 being Study Day 1 and Day -1 being the day prior to Study Day 1.

#### 7.1.2 Definition of Study Visit Windows

All data will be categorized based on the scheduled visit at which it was collected. These visit designators are predefined values that appear as part of the visit tab in the eCRF.

#### 7.1.3 Conventions for Missing Adverse Event Dates

Missing or partial AE start dates will be imputed according to the following rules.

**Table 7.1 Imputation Rules for Missing AE Start Dates**

Non-missing	Missing	Estimated
Month and Year	Day	
Day of first dose date of STUDY DRUG, if month and year of onset date are the same as month and year of date of first dose.
 
The last day of the month, if the month and year of onset date are before the month and year of date of first dose of STUDY DRUG.
 
The first day of the month, if the month and year of onset date are after the month and year of date of first dose of STUDY DRUG.

Year	Day and Month	
Day and month of first dose date of STUDY DRUG, if the year of onset date is the same as the year of date of first dose of STUDY DRUG.
 
December 31st, if the year of onset date is prior to the year of date of first dose of STUDY DRUG.
 
January 1st, if the year of onset date is after the year of date of first dose of STUDY DRUG.

	Day, Month and Year	Date of first dose of STUDY DRUG

Missing or partial AE stop dates will be imputed according to the following rules. If only the day is missing, use 15th of the month; if both month and day are missing, use June 30th. For a record with a start date and a partial stop date, if the estimated stop date is before the start date, the stop date will not be estimated.

If AE stop date is not missing and AE stop date < estimated start date, let estimated onset date = AE stop date.

All dates presented in listings are recorded dates without imputation.

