### 7.11.1 Adverse Events

AEs will be tabulated according to the Medical Dictionary for Regulatory Activities (MedDRA) Version 19.0 by system organ class, high-level terms, preferred terms and intensity. AEs with missing start and/or end dates will be imputed according rules specified in Section 7.1.3.

Treatment emergent AE is defined as any AE that occurs after administration of the first dose of study treatment and up through 30 days after the last dose of study drug. Patients with the same AE more than once will have that event counted only once within each body system, once within each high-level term, and once within each preferred term. AEs will be summarized and will include the following categories:

- Treatment-emergent AEs
- Drug-related treatment-emergent AEs
- Grade 3 or higher treatment-emergent AEs
- Grade 3 or higher drug-related treatment-emergent AEs
- Treatment-emergent AEs resulting in study drug discontinuation
- SAEs
- AEs of peripheral neuropathy identified by the broad search MedDRA SMQ "Peripheral neuropathy"

Treatment-emergent AEs will be tabulated by system organ class, high-level term and preferred term. The most commonly reported treatment-emergent AEs (i.e., those events reported by  $\geq$  10% of all patients) will be tabulated by preferred term. The individual patient's information on the DLTs will be presented in a listing. Additional analyses of peripheral neuropathy may also be presented.

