#### 7.11.1.2 Peripheral Neuropathies

Peripheral Neuropathy (PN) is defined by the peripheral neuropathy SMQ broad search. The incidence of treatment-emergent PN and treatment-emergent treatment-related PN will each be summarized by preferred term and severity. Time to onset, resolution and improvement of PN events will be summarized. Individual plot by preferred term for treatment-emergent peripheral neuropathy (SMQ) will also be presented.

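### A partial AE stop date gets no estimate when the fixed 15th or June 30th falls before the start, even if the event is known to have ended later in that same month or year

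*SAP*

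**What the plan says.** The text under Table 7.1 in SAP Section 7.1.3 gives the stop-date rule: "If only the day is missing, use 15th of the month; if both month and day are missing, use June 30th". It then limits the rule: "if the estimated stop date is before the start date, the stop date will not be estimated". No fallback date follows.

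The same section treats the mirror conflict, a known stop date before an estimated start, differently: "If AE stop date is not missing and AE stop date < estimated start date, let estimated onset date = AE stop date". In that case the estimate is moved to the known date and kept.

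Listings are not affected: "All dates presented in listings are recorded dates without imputation".

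Section 7.11.1 carries these rules into the AE analysis: "AEs with missing start and/or end dates will be imputed according rules specified in Section 7.1.3". The planned summary most likely to need an AE end date is in Section 7.11.1.2: "Time to onset, resolution and improvement of PN events will be summarized". Section 7.1.4 repeats the stop-date wording for concomitant medications.

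**The concern.** A partial stop date says that the event ended, and it bounds when. If the recorded stop month equals the start month, the end lies between the start date and the last day of that month. The rule tries one fixed date, finds that it lies before the start, and then makes no estimate, although a bounded one was available.

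The loss is not random. With only the day missing, it falls on short events that start after the 15th and end in the same month. With day and month missing, it falls on events that start after June 30th and end in the same year. A summary of time to resolution that relies on imputed stop dates would therefore lose short events more often than long ones. The neuropathy summary in Section 7.11.1.2 is the planned analysis where this could matter.

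**Working it through.** The SAP gives no figure on this point to reproduce. The check applies the Section 7.1.3 rule to each calendar day of a 365-day year.

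**Inputs from the SAP:** the 15th (day missing), June 30th (day and month missing), and no estimate if that date precedes the start.

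**Assumptions, not in the SAP:** every start day is equally likely; the start date is complete; the event lasts *D* days, so that it stops *D* days after the start; and the event has a partial stop date of the stated type.

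**Examples.**
- Start 20 March, stop recorded as March of the same year. Estimate 15 March, before the start, so no date. The true stop lies between 20 and 31 March.
- Start 10 March, stop recorded as March. Estimate 15 March, kept.
- Start 3 August, only the stop year known and equal to the start year. Estimate 30 June, before the start, so no date.

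**Day missing.** In a month of *n* days the date is lost if the start falls after day 15 and the stop is still in that month. That is max(0, *n* − 15 − *D*) start days per month. If the stop falls in a later month, the 15th of that month is after the start and nothing is lost.
- *D* = 0: 365 − 12 × 15 = 185, and 185/365 = 51%
- *D* = 1: 185 − 12 = 173, and 173/365 = 47%
- *D* = 3: 185 − 36 = 149, and 149/365 = 41%
- *D* = 7: 185 − 84 = 101, and 101/365 = 28%
- *D* = 14: seven 31-day months give 2 each, four 30-day months give 1 each, February gives 0; 18/365 = 5%
- *D* = 21 or more: 0%

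**Day and month missing.** The date is lost if the start is on or after 1 July (184 days) and the stop is in the same year, which is (184 − *D*)/365 for the durations shown.

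| Duration *D* (days) | Day missing | Day and month missing |
|---|---|---|
| 0 | 51% | 50% |
| 1 | 47% | 50% |
| 7 | 28% | 48% |
| 14 | 5% | 47% |
| 21 | 0% | 45% |
| 30 | 0% | 42% |
| 60 | 0% | 34% |

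**Sensitivity to the duration assumption.** Take exponential durations with mean μ and a uniform start in a 30-day month. The share of all day-missing events that is lost is [15 − μ(1 − e^(−15/μ))]/30.
- μ = 5: (15 − 4.75)/30 = 34%
- μ = 30: (15 − 11.80)/30 = 11%
- μ = 60: (15 − 13.27)/30 = 6%
- μ = 90: (15 − 13.82)/30 = 4%

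**Direction.** In both columns the loss falls as duration rises, steeply when only the day is missing. If lost events are dropped, those left are longer on average. If they are censored at a later date, short resolutions become long censored times. Either way the loss itself moves time to resolution upward.

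**The case against.** The strongest reply is that this is a deliberate, prespecified convention. Section 7.1 says that missing data are generally not imputed, and Section 7.1.4 uses the same rule for medications. The first part does not settle the matter, because Section 7.1 itself refers AE dates to the imputation rules of Section 7.1.3. It is true, though, that the rule contradicts nothing else in the SAP.

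Three stronger readings are tempting, and the SAP does not support them.
- A reader might infer that the affected events are reported as unresolved and that the resolution rate falls. No section says so. Section 7.11.1.2 does not state whether resolution is taken from the stop date or from a recorded outcome, nor whether an event without an analysis stop date is ongoing, censored or excluded. The rate falls only if such events are counted as ongoing.
- A reader might infer that recorded information is erased. Only the estimate is withheld, and the listings keep the recorded partial date.
- A reader might quote a loss of about 30% to 42%. That range holds only among events that start and end in the same month, which is already the subset at risk (exponential durations, means from 30 down to 5 days). Over all events with a missing stop day, the same kind of model gives 34% at a mean of 5 days and 4% at 90 days.

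The narrow reach also stands as an objection. Treatment-emergent status rests on when the event occurs ("Treatment emergent AE is defined as any AE that occurs after administration of the first dose of study treatment"), and tables of incidence, grade and seriousness need no stop date. What remains is a descriptive summary in a study of about 42 evaluable patients, with no test attached to it.

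**Conclusion.** The point holds as a minor defect of the imputation rule. When the known stop month or year equals that of the start, the rule leaves an event known to have ended without an analysis stop date, and it does so selectively. With the day missing, only short events starting after the 15th are exposed. With day and month missing, events starting after June 30th are exposed, including longer ones.

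The upward effect on time to resolution of peripheral neuropathy is conditional on that summary using the imputed stop dates, and it describes the loss alone. The percentages rest on uniform start days and assumed durations, since the SAP gives no durations of neuropathy events. The number of partial stop dates cannot be known from the SAP, so the absolute effect cannot be computed and is probably small. AE incidence tables and the primary endpoint, response rate by independent review, are unaffected.

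**What to change.** Add to Section 7.1.3: if the 15th (or June 30th) precedes the start date but the recorded stop month (or year) equals that of the start, set the stop date to the midpoint between the start date and the end of that month (or year), capped at death or data cutoff. Leave the date missing only when the recorded stop month or year truly precedes the start.

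In the examples, 20 to 31 March is 11 days, so the midpoint, rounded down, is 25 March. From 3 August to 31 December is 150 days, so the midpoint is 17 October. No partial stop date with a known year would then lack an analysis date unless the record contradicts itself.

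The midpoint is preferable to the later of the start date and the 15th, which gives every affected event a duration near zero, and to the last day of the period, which gives the longest possible duration.

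Add to Section 7.11.1.2 that any event with a recorded partial stop date counts as resolved. Section 7.1.4 can be aligned for consistency.

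The cost is about one sentence in each place and a line or so of code. The downside is that the imputed duration remains approximate, most of all when only the year is known.

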#### **7.1.4 Conventions for Missing Concomitant Medication Dates**

If only the day is missing, use 15th of the month; if both month and day are missing, use June 30th. For a record with a start date and a partial stop date, if the imputed stop date is before the start date, the stop date will not be estimated.

All dates presented in listings are recorded dates without imputation.

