#### **7.6 Medication History and Concomitant Medications**

Medication history including prior antineoplastic therapy, prior surgery, prior radiation, and prior transplant procedure information will be presented in by-patient listings. The number and percentage of patients with any prior event will be tabulated by dose and by disease type.

Concomitant medications will be coded by preferred term using the World Health Organization (WHO) Drug Dictionary (March 2012 Version). Concomitant medication is defined as any medication administered between the first and the last days (inclusive) of the study. The number and percentage of patients taking concomitant medications from signing of informed consent form through 30 days after the last dose of brentuximab vedotin will be tabulated by Anatomical Therapeutic Chemical (ATC) classification pharmacological subgroup and WHO drug generic term.

Patients are counted once for each ATC pharmacological subgroup and once for each WHO preferred term.

Concomitant procedures will not be coded, but will be presented in a by-patient listing.

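### SAP 7.1.4 can impute a medication's start after its recorded stop, and its fixed dates can decide, without regard to consent or last dose, whether a drug is counted as concomitant

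*SAP*

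**What the plan says.** SAP 7.1 gives two places where date imputation is set out: "Imputation rules for missing dates of AEs and concomitant medications are detailed in Sections 7.1.3 and 7.1.4". Section 7.1.4 holds the whole medication rule: "If only the day is missing, use 15th of the month; if both month and day are missing, use June 30th". It does not separate start dates from stop dates and mentions neither consent nor first or last dose. Its one check concerns a partial stop in a record that has a start date: "if the imputed stop date is before the start date, the stop date will not be estimated".

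Section 7.6 makes table membership depend on dates. It states: "Concomitant medication is defined as any medication administered between the first and the last days (inclusive) of the study". The tabulation covers drugs taken "from signing of informed consent form through 30 days after the last dose of brentuximab vedotin". Each patient counts once per drug class and once per drug term.

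Section 7.1.3 treats adverse event (AE) starts differently. When only the day is missing, the first entry in Table 7.1 is "Day of first dose date of STUDY DRUG, if month and year of onset date are the same" as those of first dose. The text below the table adds that an estimated onset falling after a known AE stop is reset to that stop. For AE stop dates, 7.1.3 uses the same 15th/June 30th rule and the same check as 7.1.4.

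**The concern.** A drug belongs in the 7.6 table if its use overlaps the window. The stop date shows whether use reached consent, and the start date shows whether use began before the window closed. A fixed calendar point that ignores both boundaries can therefore settle membership by where consent or last dose happens to fall in the month or year.

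The start-date side is the clearer fault. The check in 7.1.4 is triggered only by a partial stop, so nothing prevents a partial start from being placed after a complete, recorded stop. The record then contradicts itself, and in some cases a drug known to have been taken on study drops out. At stake is the accuracy of the plan's only tabulation of concomitant medication.

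**Working it through.** The plan gives no figure on this point, so there is none to reproduce. Inputs are the 7.1.4 rule and its check, the 7.6 window, and the 7.1.3 correction for AEs. I take a drug as counted when its start is on or before window close and its stop is on or after consent. The SAP does not write this test out, but it is the natural reading of 7.6.

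**(a) Partial start, recorded stop**

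- Start recorded as year only; stop 10 February of that year; consent in January; window closes in March.
- Imputed start: 30 June, which is after the stop. The 7.1.4 check does not apply because the stop is complete.
- The imputed start is after window close, so the drug is not counted. Yet the recorded stop lies between consent and window close, so it was taken on study.
- Under the 7.1.3 correction the start would become 10 February and the drug would be counted.
- The same inversion occurs with only the day missing: a start of ‘March’ with a stop of 8 March gives a start of 15 March.
- The drug is lost only if the window closes before the imputed start. Otherwise it is still counted, but with a start after its stop.

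**(b) Partial stop in the month or year of consent**

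This applies to drugs started on or before the imputed date, or without a complete start date. For any other drug the check leaves the stop unestimated.

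- Wrongly out: consent 20 March, start 1 February, true stop 28 March recorded as ‘March’. Imputed stop 15 March, before consent. The check does not act, because 15 March is after 1 February.
- Wrongly in: consent 10 March, true stop 4 March recorded as ‘March’. Imputed stop 15 March, after consent.

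For the size, assume consent day *c* and true stop day *t* are independent and uniform over a 30-day month (an assumption, not in the SAP). That gives 30 × 30 = 900 pairs. The drug truly reaches the window if *t* ≥ *c*; the rule says it does if 15 ≥ *c*.

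- Wrongly out: *c* = 16 to 30 with *t* ≥ *c*: 15 + 14 + … + 1 = 120; 120/900 = 13.3%.
- Wrongly in: *c* = 1 to 15 with *t* < *c*: 0 + 1 + … + 14 = 105; 105/900 = 11.7%.
- Total: 225/900 = 25.0%.
- Share of true on-study use that is missed: pairs with *t* ≥ *c* number 30 × 31/2 = 465; 120/465 = 25.8%.

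For 28-day and 31-day months the split is 11.6% out and 13.4% in, and 14.2% out and 10.9% in; the total stays at about 25%. For year-only stops (365 days, 30 June = day 181):

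- Wrongly out: 184 × 185/2 = 17,020; 17,020/133,225 = 12.8%.
- Wrongly in: 180 × 181/2 = 16,290; 16,290/133,225 = 12.2%.
- Total: 25.0%.

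**(c) Effect of an inclusive rule on the same 30-day grid**

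Take the stop as the last day of its month.

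- Wrongly out: 0, because day 30 ≥ *c* always.
- Wrongly in: every pair with *t* < *c*: 0 + 1 + … + 29 = 435; 435/900 = 48.3%.

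Total error in these records therefore rises from 25.0% to 48.3%, all of it on the side of inclusion.

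**The case against.** The strongest reply is that the check in 7.1.4 already protects most on-study medication. A reader might infer that, with consent on 1 October, every year-only stop in that year is moved to 30 June and the drug lost. The SAP does not support that. A drug with a complete start after 30 June, which includes every drug with a known start on study, gets no estimated stop and is not moved out. A reader might likewise infer that about a quarter of on-study medication is dropped. The 25.8% describes only unprotected records with a partial stop in the month of consent, under uniform dates. This objection stands and sets the limits of part (b).

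Three further points also stand:

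- The contrast with the AE rules holds only for start dates. For stop dates, 7.1.3 and 7.1.4 agree.
- An error in one record changes the table only if the patient has no other qualifying record for that class or term.
- A mid-point rule makes errors of similar size in both directions. Replacing it with an inclusive rule is a preference that has to be argued.

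None of this answers part (a). The check does not cover a partial start with a recorded stop, and no other text in the SAP repairs it.

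**Conclusion.** The point holds, as a minor one. Part (a) is an error in the rule as written: an imputed start can contradict a recorded stop and, where the window has already closed, remove a drug whose on-study use is documented. This needs no distributional assumption, only the overlap reading of 7.6.

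Part (b) is a weakness of limited reach. About 25% of the exposed boundary records are misclassified if dates are uniform. How many such records will exist is unknown, and the SAP gives nothing from which to estimate it.

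A reader might also infer that safety or efficacy conclusions are at risk. The documents do not support that: the SAP links these dates to no response, survival, laboratory or AE analysis, the affected output is descriptive, and the listings print dates as recorded.

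**What to change.** Amend 7.1.4 in two respects.

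1. **Start after stop.** If an imputed start falls after a recorded stop, set the start to the stop date, as 7.1.3 does for AEs; alternatively, impute the earliest start compatible with the recorded parts. This has no statistical downside.
2. **Table membership.** State that a drug is counted unless its recorded date parts show that it ended before consent or began more than 30 days after last dose.

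The second change should carry its cost openly. It removes wrongful exclusion (13.3% to 0% of exposed records in a 30-day consent month) but raises wrongful inclusion from 11.7% to 48.3%, on the uniform-date assumption. The case for it is that missing a drug taken on study is the less acceptable error, that Table 7.1 already places AE starts at first dose when the month or year is ambiguous, and that ambiguous records stay visible in the listings. A sponsor who prefers balanced errors could keep the mid-point for partial stops and say so, but should make the first change regardless.

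The work is one paragraph of SAP text and a small programming change.
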